#### 1.4. PriMatrix Indication

PriMatrix is FDA 510(k) cleared (K061407, K083440, K100261, K131286, and K153690) for marketing in the United States and is also marketed in the European Union (CE Marked), Mexico, Canada, and many other countries.

PriMatrix® is intended for the management of wounds that include:

- Partial and full thickness wounds
- Pressure, diabetic, and venous ulcers
- Second-degree burns
- Trauma wounds — abrasions, lacerations and skin tears
- Surgical wounds — donor sites/grafts, post-Moh’s surgery, post-laser surgery, podiatric, wound dehiscence
- Tunneled/undermined wounds
- Draining wounds

## 2. Study Objective

The objective of this study is to evaluate the efficacy of PriMatrix Dermal Repair Scaffold in the closure of DFUs in subjects with DM and without significantly compromised arterial circulation in comparison to Control treatment. In addition to the efficacy data, safety associated with the management of DFUs will be evaluated, as well as medical resource utilization data.

## 3. Study Design

This is a multicenter, randomized, open-label, parallel-group clinical trial designed to establish the superior efficacy of PriMatrix over that of Control treatment in the management of DFUs in subjects with DM and adequate arterial circulation. Study enrollment will be paused once 50 subjects (25 in each treatment arm) have been enrolled in order to do an early data review. There will also be an interim analysis after 128 subjects have completed their study requirements.

### 3.1. Treatment Groups (Further defined in Section 5)

- Active Treatment – PriMatrix Dermal Repair Scaffold + Standard of Care
- Control Treatment – Standard of Care

### 3.2. Study Phases

#### 3.2.1. Screening Phase

After the informed consent process is complete, medical history will be collected and clinical assessments will be performed to determine subject eligibility for the study. If the required eligibility criteria are met, the subject will begin the two-week screening phase. During this phase, the subject will receive the control treatment as defined in Section 5. During the two-week screening phase, the investigator will determine if the subject continues to meet all eligibility criteria, and if confirmed, the subject will be randomized and enter the treatment phase. For detailed information, see Figure 1 and Table 3 below.

#### 3.2.2. Treatment Phase

Subjects will be randomized to receive the Active or Control Treatment in a 1:1 scenario (details can be found in Section 8.4). Efficacy evaluations during this phase include weekly investigator assessments of wound closure and planimetric evaluations of ulcer area. Safety evaluations will include AE assessments at each visit. Additionally, collection of medical resource utilization (MRU) data will occur. The randomized study treatment will be administered for up to 12 weeks or until the study ulcer has closed, as assessed by the investigator.

At the end of the treatment phase, subjects, all of whom will be considered treatment phase completers, will be assigned to one of two outcomes:

[figure not shown]
- Subjects with confirmed closed ulcers will be considered treatment successes.

- Subjects with open ulcers at the end of the treatment phase will be considered treatment failures.

Unscheduled Visits (i.e., those not specifically scheduled per protocol) are at the discretion of the investigator. If the unscheduled visit is for treatment of the target ulcer, data for that visit will be collected and reported on the Unscheduled Visit eCRF page. For detailed information, see Figure 1 and Table 3 below.

### 3.2.3. Follow-up Phase

Subjects whose ulcer is confirmed closed at the Confirmation Visit (i.e., 1 week after closure is observed) will return to the clinic 4-weeks later for a follow-up visit (28 ± 3 days) to evaluate if the ulcer has remained closed. For detailed information, see Figure 1 and Table 3 below.

### 3.3. Study Duration

A subject can participate in the study for up to 136 days in total with the allowed time range for visits during the treatment phase.

## 4. Study Population: Eligibility Criteria

### 4.1. Inclusion Criteria

Subjects are required to meet all of the following criteria for enrollment into the study and subsequent randomization:

1. The subject has signed and dated an informed consent form.
2. In the opinion of the investigator, subject is able and willing to comply with study procedures, including study visits, study dressing regimens and compliance with study required off-loading device.
3. The subject is  $\geq 18$  years of age.
4. The subject, if female of child-bearing potential, must not be pregnant. To document pregnancy status, subject statement is acceptable.
5. The subject has Type I or Type II diabetes mellitus with investigator-confirmed glycosylated hemoglobin (HbA1c) of  $\leq 12\%$  within 3 months prior to screening visit.
6. The subject has at least one diabetic foot ulcer that meets ALL of the following criteria:
  - Ulcer which has been in existence for a minimum of two weeks, prior to signing the Informed Consent Form for trial participation.
  - Ulcer is a partial or full thickness diabetic foot ulcer without capsule/tendon/bone exposure.
  - Ulcer does not have tunneling, undermining, or sinus tracts that necessitates surgical OR debridement and/or penetrates to capsule/tendon/bone.
  - Ulcer is located on the foot or ankle (with no portion above the top of the malleolus).
  - Ulcer size (area) is  $\geq 1 \text{ cm}^2$  and  $\leq 12 \text{ cm}^2$  post-debridement.
7. There is a minimum 1 cm margin between the qualifying study ulcer and any other ulcer on that same foot, post-debridement.
  - If the subject has more than one ulcer that meets the eligibility criteria, the ulcer designated as the study ulcer will be at the discretion of the investigator.
8. The subject has adequate vascular perfusion of the affected limb as defined by at least one of the following:
  - Ankle-Brachial Index (ABI)  $\geq 0.65$  or  $\leq 1.2$ , performed within 3 months of screening,
  - Toe pressure (plethysmography)  $> 50 \text{ mmHg}$  at time of screening,
  - TcPO2  $> 40 \text{ mmHg}$  at time of screening
9. The subject or responsible caregiver is willing and able to maintain required applicable dressing changes as well as study required off-loading/protective device for the duration of the study.

### 4.2. Exclusion Criteria

Subjects will not be enrolled in the study if any of the following criteria are met:

1. The subject was previously randomized and treated under this clinical study protocol.
2. The subject has suspected or confirmed gangrene or ulcer infection of the study ulcer or receiving systemic antibiotics for the treatment of such.
3. The subject has suspected or confirmed osteomyelitis of the foot with the study ulcer.
4. The subject has a history of hypersensitivity to bovine collagen, as determined by prior medical history.

5. The subject has participated in another clinical trial involving a device or a systemically administered investigational study drug/treatment within 28 days of randomization.
6. The subject has received, within 28 of signing Informed Consent Form, or is scheduled to receive during study participation, a medication or treatment which is known to interfere with or affect the rate and quality of ulcer healing (e.g., systemic steroids, immunosuppressive therapy, autoimmune disease therapy, dialysis, radiation therapy to the foot, vascular surgery, angioplasty, or thrombolysis).
7. The subject has a history of bone cancer or metastatic disease of the affected limb, radiation therapy to the foot, or has had chemotherapy within the 12 months prior to signing Informed Consent Form for trial participation.
8. In the opinion of the investigator, the subject has a history of, or is currently diagnosed with, any illness or condition, other than diabetes, that could interfere with ulcer healing (e.g., end-stage renal disease, severe malnutrition, liver disease, aplastic anemia, connective tissue disorder, acquired immune deficiency syndrome, HIV positive, or sickle cell anemia).
9. In the opinion of the investigator, the subject has unstable Charcot foot or Charcot with bony prominence that could inhibit ulcer healing.
10. The subject has ulcers secondary to a disease other than diabetes (e.g., vasculitis, neoplasms, or hematological disorders).
11. In the opinion of the investigator, the subject has excessive lymphedema that could interfere with off-loading and/or ulcer healing.
12. The study ulcer has received ulcer dressings that included growth factors, engineered tissues, or skin substitutes within 28 days of randomization or is scheduled to receive treatment during the study (e.g., Regranex, Dermagraft, Apligraf, EpiFix, GraftJacket, OASIS, Omnigraft, or Integra BMWD).
13. At the end of the screening phase and based on planimetric assessment, the area of the study ulcer after sharp debridement has decreased by more than 30% over the two-week screening period.

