5.16. Method for Assigning Eligible Subjects to Treatment (i.e., Randomization)

Once it has been determined that a subject meets all eligibility criteria, subjects will be assigned to one of the following treatment groups, based on a randomization schedule provided by the sponsor.

Randomization is accomplished through the Clindex EDC system. After entering your name and password, you will go into the RDE System and click on Subject List or Visit Manager. After selecting the subject to be randomized, click on the Randomization eCRF in the Randomization Visit. You will be asked to answer the following:

- Did the subject meet all eligibility criteria?
  - Select Yes if eligible
  - Select No if not eligible
- Is the percent ulcer reduction  $\leq 30\%^*$  since the initial screening visit?
  - Select Yes if the ulcer decreased in size less than or equal to 30% **or** if the ulcer got bigger
  - Select No if the area of the ulcer decreased in size more than 30% during the screening period
  - Enter the size of the decrease or increase
- Is the area of the study ulcer between 1cm^2 and 12cm^2\*?
  - Select Yes if between 1 and 12cm^2

- Select No if not between 1 and 12cm^2
- Enter the size of the ulcer area.

***\*Important: Rounding up or down is not allowed to achieve eligibility. For instance, if the ulcer decreased 30.1% between SV1 and Randomization, the subject is still ineligible for randomization. Similarly, if the area of the wound is 0.99cm^2 at either SV1 or Randomization, the subject is ineligible.***

After all of the questions have been answered, you will click on the Save button. Click “Yes” on each of the following pop-up screens. A third screen will pop up with the randomization group: Active or Control. The active treatment is the PriMatrix product (see Section 5.17 below). The control treatment is SOC that has been used during the past two screening visits.

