#### 6.1.2. Screening Visit 2 (SV2)

Screening Visit 2 assessments and procedures are summarized in Table 3. At SV2 the following data will be collected, and procedures performed:

1. Review Inclusion and Exclusion criteria for continued eligibility
2. Medical Resource Utilization assessment will be performed (see Section 5.3 for specific information on how to perform this assessment).
3. Ask subject about compliance with the treatment during the previous week
4. Perform ulcer assessments
5. Photograph the study ulcer pre-debridement
6. Perform ulcer measurements pre-debridement
7. Perform sharp debridement of the study ulcer, if necessary per investigator discretion.
8. Photograph of the study ulcer post-debridement, if debridement occurred.
9. Perform ulcer measurements post-debridement, if debridement occurred.
10. Apply SOC treatment to the ulcer (see Section 5.11 for specific application processes)
11. Discuss treatment compliance with the subject
12. If appropriate, apply the off-loading/protective device and discuss compliance with its use
13. Document applicable Concomitant Medications noted by the subject or seen within the subject's medical records (see Section 5.14 for information on which medications require documentation).
14. Document any applicable AEs as noted by the subject or as documented in their medical record (see Section 5.15 for information on which AEs require documentation).

*\* Remember to schedule the next visit for Randomization/TV 1 (Day 0), 14±3 days from SV1.*

*IMPORTANT: If a subject initially fails to meet inclusion/exclusion criteria, e.g., because the ulcer is too large or is infected, and is later reconsidered for participation, the subject will be re-*

*consented and assigned a new screening number at the time of re-screening. Subjects who fail their first screening attempt may be re-screened a maximum of one time and may be entered into the study a second time if they are found to meet ALL inclusion and NO exclusion criteria.*

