### 6.2.1. Randomization/TV 1 (Day 0)

1. Review Inclusion and Exclusion criteria for eligibility
  - *Important: The final exclusion criteria will only be determined after debridement and measurement as detailed below in this Section.*
2. Medical Resource Utilization assessment will be performed (see Section 5.3 for specific information on how to perform this assessment).
3. Ask subject about compliance with the treatment during the previous week
4. Perform ulcer assessments
5. Photograph the study ulcer pre-debridement
6. Perform ulcer measurements pre-debridement
7. Assess the ulcer for wound closure status
  - If the wound is closed, the subject is exited at this point; complete the study exit form.
8. Perform sharp debridement of the study ulcer
9. Photograph of the study ulcer post-debridement
10. Perform ulcer measurements post-debridement
11. Document ulcer size reduction
12. Complete the randomization process in the EDC system.
13. Apply either SOC or the Active treatment to the ulcer, depending on the cohort that is assigned during the randomization process (see Section 5.16 for specific application processes)

14. Discuss treatment compliance with the subject
15. If appropriate, apply the off-loading/protective device and discuss compliance with its use
16. Document applicable Concomitant Medications noted by the subject or seen within the subject's medical records (see Section 5.14 for information on which medications require documentation).
17. Document any applicable AEs as noted by the subject or as documented in their medical record (see Section 5.15 for information on which AEs require documentation).

*\* Remember to schedule the next visit for Treatment Visit Week 2, 7±3 days from Randomization/TV 1.*

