### 8.12.6. Supportive Analysis

To assess the robustness of the primary analysis results, supportive analysis will be conducted using the PP population. Statistical methodology for the supportive analyses will be the same as that of the primary analysis, with the exception of the analysis population used. The PP population will be used for the supportive analysis while ITT population will be used for the primary analysis. Subjects in these populations with no post randomization data for the primary endpoint will be considered NOT CLOSED, i.e., treatment failures, in this analysis.

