10. ANALYSIS POPULATIONS

10.1. Intent-to-Treatment Population

The Intent-to-Treat (ITT) population is defined as all subjects randomized and received treatment after randomization. The ITT population will be used for the analysis of exploratory and safety endpoints.

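### Exclusion criterion 1 does not expressly bar a second randomisation of a subject who was randomised but not treated, and the SAP's ITT set drops such a subject

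*Protocol*

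**What the plan says.** Criterion 1, in the synopsis and in protocol 4.2, excludes a person on this ground: "The subject was previously randomized and treated under this clinical study protocol". No other criterion mentions previous randomisation in this trial.

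Protocol section 3 describes the design: "This is a multicenter, randomized, open-label, parallel-group clinical trial". Under 5.16 the EDC system reveals the arm: "A third screen will pop up with the randomization group: Active or Control". In 6.2.1 the randomisation step is item 12, and item 13 reads "Apply either SOC or the Active treatment to the ulcer, depending on the cohort that is assigned during the randomization process".

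On re-entry, 6.1.2 says "Subjects who fail their first screening attempt may be re-screened a maximum of one time"; such a subject is re-"consented and assigned a new screening number at the time of re-screening".

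On subjects who leave, protocol 6.2 starts the treatment phase at randomisation. Sections 7 and 8.12.3 make a subject who withdraws without closure a treatment failure who is not replaced, and SAP 11.5 and 11.6 agree. Protocol 8.12.6 adds: "Subjects in these populations with no post randomization data for the primary endpoint will be considered NOT CLOSED".

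On analysis sets, protocol 8.10.1 takes ITT as every randomised subject. SAP 10.1 instead takes "all subjects randomized and received treatment after randomization", SAP 10.3 makes the Safety set identical to it, and SAP 10.4 defines the PEP by randomisation date with no treatment condition.

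**The concern.** Randomisation protects the comparison only if the first assignment is final. Here the investigator and subject see the arm before anything is applied, the primary endpoint is investigator-assessed, and the one criterion on previous participation adds a second condition, treatment, that an untreated subject does not meet. If such a person were enrolled again, preference could partly replace chance. Without a one-entry-per-person rule, that person could also contribute two records to an analysis that assumes independent subjects.

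The SAP's ITT wording raises a related problem that does not depend on re-entry. A subject who leaves after seeing the arm may do so because of it. Removing that subject from the set used to show robustness conditions the set on an event after randomisation.

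**Working it through.** **1. The plan's own design figures.** None is in dispute. With 46% and 26% closure, 102 per group, a look at half the information, nominal two-sided levels of 0.031 and 0.028 and pooled variance, the two-look calculation gives power 0.803, early-stop probability 0.479 (as stated) and overall alpha 0.0502. Rewording criterion 1 changes none of these.

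**2. Is a second randomisation barred?**
- Criterion 1: not met by a randomised, untreated subject.
- Section 6.1.2: grants one re-screen to screen failures. A randomised subject has passed screening, so the route does not apply on its terms, but the section does not say that re-screening ends at randomisation.
- Sections 7 and 8.12.3: fix the status of the first entry and rule out replacement. They do not mention a second entry by the same person.

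The result is no express bar and no express route.

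**3. Where an untreated subject falls.**

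| Set | Condition | Untreated subject |
|---|---|---|
| Protocol ITT (8.10.1) | randomised | in |
| SAP ITT (10.1) | randomised and treated | out |
| SAP Safety (10.3) | same as SAP ITT | out |
| PEP (10.4) | randomised by 3/3/2020 | in |

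The PEP carries the primary and secondary endpoints. The SAP ITT set carries the exploratory and safety endpoints and the prognostic-factor analysis in 11.4, which is meant to support the primary result.

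**4. What a redraw could do, under assumptions.** Protocol 8.4 gives mixed blocks of 2 and 4. Assume that the two sizes are equally likely, that blocks run within site-by-ulcer-size cells, and that nobody else enters the cell in between. Averaged over the six positions in one block of each size, the chance that the next assignment is the opposite arm is

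(1 + 0.5 + 3 × 2/3 + 0.5) / 6 = 0.667.

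One redraw then raises the chance of ending in a preferred arm from 0.50 to 0.5 + 0.5 × 0.667 = 0.83 for that person.

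Across the trial, if a share q of control-assigned subjects were redrawn once at an independent 1:1, the share ending in Active would be 0.5 + 0.5 × q × 0.5. This is 50.5%, 51.3% and 52.5% for q = 2%, 5% and 10%.

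**5. Failure records in control.** SAP 11.1.1 puts 207 patients in the PEP, so about 103 per arm. With 26% closure, 0.26 × 103 = 26.78 closures. Adding k untreated failures gives 26.78 / (103 + k):
- k = 2: 25.5%
- k = 4: 25.0%
- k = 6: 24.6%

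Against 46%, the difference moves from 20.0 to 20.5, 21.0 and 21.4 points. A subject who leaves untreated and never returns produces the same shift, because the plan counts that subject as a failure anyway. What re-entry would add is a second record for the same person and selection into the other arm. The values of q and k are illustrative; the documents supply none.

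**The case against.** The strongest reply is that silence is not permission. The only written re-entry route is for screen failures, and the plan already gives a randomised subject who leaves a final status. Re-entry would also need new consent, another two weeks of screening with no more than 30% area reduction, and the investigator's judgement that someone who had just declined an arm is able and willing to comply. This stands, and it makes the risk narrow.

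It can also be argued that every randomised subject has already had control dressings during screening and so counts as treated. If that is the meaning, the two words add nothing and deleting them loses nothing.

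A reader might infer more than the documents support:
- That the plan allows re-randomisation, or that the allocation is broken. No passage allows it and no case is reported.
- That two entries could not be linked. The new screening number does not erase the link: sites keep a screening and randomisation log (12.3) and collect date of birth (5.4).
- That the PEP would count one person twice. SAP 10.4 and 11.1.1 speak of subjects and patients, not screening numbers. The rule is unstated, and double counting is not prescribed.
- That the incentive runs only against control. Control does repeat the screening regimen, but some subjects may decline a bovine scaffold that can be fixed with staples or sutures (5.17.3).

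Finally, SAP 10.4 records a decision to end screening and enrolment, so rewording the criterion now has little practical effect. That also stands.

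**Conclusion.** There is a real but small wording gap: criterion 1 does not make the first assignment final, and that is left to inference in an open-label trial with an investigator-assessed endpoint. The size of any effect is unknown. Under the assumed counts of 2 to 6 in the PEP, the control rate moves by 0.5 to 1.4 points against a planned 20-point difference, and that shift is not specific to re-entry.

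The ITT mismatch between SAP 10.1 and protocol 8.10.1 is certain from the text. Its reach is limited: the primary and secondary analyses use the PEP, which keeps untreated subjects, while the robustness analysis in SAP 11.4 loses them.

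**What to change.** **SAP (live now).**
- In 10.1, define ITT as all randomised subjects, analysed as assigned, to match protocol 8.10.1.
- In 10.3, stop defining Safety as identical to ITT; keep it as treated subjects, as in protocol 8.10.3, and run the safety analyses on it.
- In 10.1 and 10.4, state that each person is counted once, in the arm first assigned.
- Before lock, check for duplicate persons by date of birth, site and randomisation log, and report the result even if it is zero.

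**Protocol (for the record or any further version).** Delete *and treated* from criterion 1 in the synopsis and in 4.2. Add one sentence to 6.1.2 saying that re-screening applies only before randomisation.

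**Cost.** A few words and one data check. A randomised but untreated subject cannot be enrolled again and counts as not closed in the arm first assigned. Alpha, sample size and power are unchanged.
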